### **6.3.3. Health Related Quality of Life Surveys**

Quality of life surveys included in this study are Short Form-36 (SF-36), Chronic Liver Disease Questionnaire (CLDQ-HCV), and Work Productivity and Activity Impairment Questionnaire: Hepatitis C (WPAI: Hepatitis C) which will be completed by subjects and collected at each visit. Subjects should read the questionnaires and write/mark answers directly onto the paper questionnaires prior to any other study assessments. Sites will mail completed surveys with a transmittal sheet to a data entry vendor as directed.

### **6.3.4. Limited Physical Exam**

The limited physical exam includes height (at Day 1 only) and weight measurements for calculation of BMI. Assessments for ascites and encephalopathy will be conducted at each visit for calculation of CTP score.

### **6.3.5. Liver Disease Assessment**

Information will be collected at each visit for a liver disease assessment. Day 1 assessment will include determining whether any of the following have occurred since the last parent-protocol study visit prior to Day 1 for patients who achieved SVR in a Gilead-sponsored study or since the completion of the HCV therapy resulting in SVR prior to Day 1 for subjects who enroll after receiving an all-oral SOF-based regimen outside a clinical study. Assessment at all other study visits will include determining whether any of the following have occurred since the last study visit through Week 240 or early termination (unless otherwise specified). For subjects enrolled having received an all-oral SOF-based regimen outside a clinical study, the screening liver disease assessment will include the start and stop date of any clinical liver-associated events.

- Imaging of the liver performed as part of standard of care (eg, CT, MRI, or Ultrasound; results, if available)
- Liver biopsy or endoscopy to evaluate for varices (results, if available)
- Clinical liver-associated events including reports of hepatic encephalopathy, hepatocellular carcinoma, hepatorenal syndrome, hepatopulmonary syndrome, portopulmonary hypertension, hepatic hydrothorax, bleeding varices or spontaneous bacterial peritonitis
- Liver transplant (at any time prior to Day 1 and during the study)

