### **3. STUDY DESIGN**

#### **3.1. Study Design**

This Registry will enroll cirrhotic subjects with or without decompensated liver disease who have achieved an SVR after receiving a SOF-based regimen without IFN while participating in a Gilead-sponsored HCV study; or, at a subset of sites preselected by Gilead, who have previously received an all-oral SOF-based regimen outside a clinical study. For subjects enrolling from a Gilead parent protocol, the definitions of cirrhosis and of SVR are defined in the Gilead-sponsored treatment protocol.

Subjects who enroll after receiving an all-oral SOF-based regimen outside a clinical study, will have had cirrhosis confirmed prior to initiation of HCV treatment.

In order to manage the total study enrollment, Gilead Sciences, Inc. will determine which treatment protocols and sites to include in this SVR Cirrhosis Registry study. At its sole discretion, Gilead may at any time discontinue enrollment and/or early withdraw individual subjects from individual treatment protocols prior to study completion (upon written notice to the site) regardless of the progress or outcome of the protocol assessments performed.

Once enrolled, subjects will be followed for up to 5 years. For subjects rolling over from a Gilead parent protocol, a Day 1 visit will be scheduled within approximately 60 weeks from a subject's projected SVR 24 visit in the treatment protocol, or subjects may enroll from the GS-US-248-0122 SVR registry study at any time with Sponsor approval. For subjects who enroll after receiving an all-oral SOF-based regimen outside a clinical study, a Day 1 visit will be scheduled within approximately 2 years from the subject's SVR 12 date. Visits will occur at Day 1 and then every 24 weeks at Weeks 24, 48, 72, 96, 120, 144, 168, 192, 216 and 240.

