#### **3.2. Discontinuation Criteria**

Registry participation will be discontinued in the following instances:

- Subjects who experience virologic relapse or re-infection defined as HCV RNA > LLOQ on two samples collected at least one week apart;
- Subjects who have a liver transplant;
- Subjects who request to discontinue for any reason; it is important to clearly determine and document the specific reason for withdrawal of consent;
- Discontinuation of the Registry and/or subjects at the request of Gilead, regulatory agency or an Institutional Review Board (IRB)/Independent Ethics Committee (IEC).

If a subject meets withdrawal criteria or discontinues participation for any reason, the subject should complete an Early Termination visit.

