### **8.6.1. Primary Analysis**

The proportion of subjects who maintain an SVR through Week 240 will be estimated using a Kaplan-Meier model, allowing for censored observations due to early discontinuation from the Registry.

The proportion of subjects who develop clinical progression or regression of liver disease through Week 240 will be estimated using a Kaplan-Meier model, allowing for censored observations due to early discontinuation from the Registry.

The proportion of subjects who develop HCC through Week 240 will be estimated using a Kaplan-Meier model, allowing for censored observations due to early discontinuation from the Registry.

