### **8.7.2. Adverse Events**

Clinical and laboratory adverse events will be coded using the Medical Dictionary for Regulatory Activities (MedDRA). System Organ Class (SOC), High-Level Group Term (HLGT), High-Level Term (HLT), Preferred Term (PT), and Lower-Level Term (LLT) will be attached to the clinical database.

Events will be summarized by the date of onset for the event. An adverse event is defined as an event that begins or worsens on or after the date the ICF is signed through study completion or study discontinuation and is classified as related to study procedure.

Adverse events, including SAEs by the above definition, will be listed by subject. The frequency of subjects who experience adverse events will be summarized overall, by treatment regimen and by severity.

SAEs that do not meet the above definition will not be captured or summarized.

Data listings will be provided for subjects who discontinued the study due to an adverse event by the above definition.

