6.1.3.2. Proportion of Participants Who Develop Liver Disease Progression or Regression

6.1.3.2.1. Liver Disease Assessment Including Hepatocellular Carcinoma

Events related to liver disease progression include:

- Hepatic encephalopathy
- Hepatocellular carcinoma (HCC)
- Hepatorenal syndrome
- Hepatopulmonary syndrome
- Portopulmonary hypertension
- Hepatic hydrothorax
- Bleeding varices
- Spontaneous bacterial peritonitis
- Liver Transplant
- Ascites
- Liver-related death

Hepatic decompensation events include:

- Hepatorenal syndrome

- Hepatopulmonary syndrome
- Portopulmonary hypertension
- Hepatic hydrothorax
- Hepatic encephalopathy
- Bleeding varices
- Spontaneous bacterial peritonitis
- Ascites
- Liver-related death

Except for ascites (using data collected from liver imaging)/liver transplant/death, other events will be all collected from liver disease assessment page in eCRF. Minimal or trace ascites will not be treated as a liver event. Liver-related death will be identified by Clinical Research based on the immediate cause of death.

Participants with events related to liver disease progression that were identified prior to registry start date will be excluded from the analysis but will be listed.

Participants with De Novo HCC since registry start are defined as participants who were not identified with HCC prior to registry start and only had HCC since registry start.

Summary of participants with liver events will be provided, including the percentage of participants with events among FAS, the percentage of participants for each type of events among all the participants with events, and the percentage of participants with any event prior to registry start among FAS.

Person-time pertaining to KM analysis of time to events in this section will be calculated as: first event date (for participants who experienced events) or last day of registry (for participants who did not experience events) – registry start date + 1.

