7. SAFETY ANALYSES

Analysis of safety measures will be descriptive and will include participants in the Safety Analysis Set. All safety data collected on or after the date of enrollment through the remainder of the study will be included.

As there was no intervention in this study, only AEs related to the required procedures by this registry were recorded. Any reference to an AE or serious adverse event (SAE) in this SAP will be referring to AEs and SAEs related to procedures required by this registry. All deaths, regardless of relatedness to study procedures were recorded when available. The immediate cause and date of death were collected when available.

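### A participant whose death record gives HCC as the cause, but whose liver disease assessment page has no HCC entry, is censored as HCC-free in the De Novo HCC Kaplan-Meier estimate

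*Protocol*

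**What the plan says.** HCC through Week 240 is a primary endpoint (Protocol 8.1.2, SAP 6.1.1). Protocol 8.6.1 gives the estimator: "The proportion of subjects who develop HCC through Week 240 will be estimated using a Kaplan-Meier model", with censoring for early discontinuation.

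- **How events are found.** Protocol 3.1 sets the schedule: "Visits will occur at Day 1 and then every 24 weeks". Protocol 6.3.5 lists HCC among the clinical liver-associated events sought at each visit: "Assessment at all other study visits will include determining whether any of the following have occurred since the last study visit".
- **What the analysis uses.** SAP 6.1.3.2.1 names the source: "Except for ascites (using data collected from liver imaging)/liver transplant/death, other events will be all collected from liver disease assessment page in eCRF".
- **Closing assessment.** For a participant who discontinues, Protocol 3.2 says "the subject should complete an Early Termination visit", and Protocol 6.2.4 includes the liver disease assessment in that visit.
- **Safety data.** Adverse events are limited to those related to registry procedures. Of other serious events, Protocol 8.7.2 says "SAEs that do not meet the above definition will not be captured or summarized".
- **Deaths.** SAP 7 says all deaths were recorded when available, whatever their relation to procedures, and "The immediate cause and date of death were collected when available". SAP 6.1.3.2.1 has Clinical Research use the immediate cause to identify liver-related death, which is an event in the progression and hepatic decompensation lists.
- **De Novo HCC.** SAP 6.1.3.2.1 defines it as HCC since registry start with none identified before. Participants without an event contribute person-time to their last day of registry.

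**The concern.** The HCC endpoint has one data source, and that source is a look-back question put at visits 24 weeks apart. A participant who dies between visits has no next visit and cannot attend an Early Termination visit. Neither document says that the page is to be completed from records after death, and the serious adverse event route is closed to HCC. The cause of death is collected and reviewed, but no rule carries an HCC death across to the HCC endpoint.

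The same participant could therefore appear as a liver-related death from HCC in one table and as HCC-free in the primary HCC estimate. The cases at risk are the rapidly fatal ones, and the censoring is then brought about by death from the very event being counted. The error runs in one direction only, and the SAP plans no sensitivity analysis that would show it.

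**Working it through.** The documents give no sample size, event count or post-HCC survival, so there is no figure of the plan to reproduce. The check has two parts.

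**1. Following one case through the rules as written.** A participant has no HCC before registry start and none reported at Week 72. HCC is diagnosed at Week 78 and the participant dies at Week 90, before the Week 96 visit.

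- Liver disease assessment page: the last entry is Week 72, with no HCC. Unless the site adds an entry after death, none exists.
- Serious adverse events: HCC is not related to a registry procedure, so it is not captured (Protocol 8.7.2).
- Death record: the death is recorded, with HCC as immediate cause if that information is available (SAP 7).
- Liver-related death: the participant counts in the progression and decompensation analyses (SAP 6.1.3.2.1).
- De Novo HCC: there is no entry on the page and no rule drawing on the death record, so the participant is censored at the last day of registry.

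**2. An upper-bound illustration of size.**

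Inputs:
- Visit interval τ = 24 weeks = 168/365.25 = 0.460 years (Protocol 3.1).
- Follow-up T = 240 weeks = 1680/365.25 = 4.60 years.
- HCC rate h = 2% per year. Protocol 1.1 gives 1 to 4% per year for established cirrhosis, which is not a post-SVR rate.
- Death hazard after HCC diagnosis λ = 0.2, 0.4 or 1.0 per year. These are assumptions, not in the documents. One-year mortality, 1 − exp(−λ), is 18%, 33% and 63%.
- Diagnosis uniform within an interval, exponential survival afterwards, no missed visits, and every such case left unrecorded. The last condition makes this an upper bound for a given λ.

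Share of HCC events followed by death before the next visit: m = 1 − (1 − exp(−λτ))/(λτ).

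- λ = 0.2: λτ = 0.092, m = 4.5%
- λ = 0.4: λτ = 0.184, m = 8.7%
- λ = 1.0: λτ = 0.460, m = 19.8%

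Rounded from unrounded values, these are about 4%, 9% and 20%.

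On the Kaplan-Meier scale, with deaths censored as planned, the full Week 240 estimate is 1 − exp(−hT) and the recorded estimate is 1 − exp(−h(1 − m)T):

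| h per year | Full | Recorded, λ = 0.2 | λ = 0.4 | λ = 1.0 |
|---|---|---|---|---|
| 1% | 4.5% | 4.3% | 4.1% | 3.6% |
| 2% | 8.8% | 8.4% | 8.1% | 7.1% |
| 4% | 16.8% | 16.1% | 15.5% | 13.7% |

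At 2% per year the shortfall is about 0.4, 0.7 and 1.7 percentage points (8.79% against 8.41%, 8.06% and 7.11%).

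**The case against.** A reader might infer that HCC and most decompensation events can be recorded only at a visit the participant attends, so that whatever arises between the last visit and death is lost. The documents do not support that.

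- **Attendance is inferred, not required.** Protocol 6.3.5 collects information, including reports of events and standard-of-care results. Nothing forbids a site from completing the page or the Early Termination form from records after a death. SAP 4.4 shows that some visits were virtual, and the eCRF completion guidelines are not among the documents.
- **The composites are largely protected.** A death classed as liver-related still counts in the progression and decompensation analyses. What is lost there is the event type and its earlier date. The protection does depend on the immediate cause being available and judged liver-related.
- **Survivors are recovered.** Anyone who reaches a later visit or an Early Termination visit is picked up by look-back, and SAP 3.7 dates HCC to the earliest diagnosis. The affected group is narrow.
- **The size rests on assumptions.** The post-HCC hazards are not in the documents, the HCC rate is not a post-SVR rate, and the model takes every such case as unrecorded, which is the open question. The registry is descriptive, with no hypothesis test.

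All of this stands, and it limits the point to HCC. It does not remove the point. SAP 6.1.3.2.1 states a single-source rule, and under that rule an HCC death with no entry on the page is not an HCC event. If some sites do complete the page after death, practice may differ between sites, which is a further reason to state a rule.

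**Conclusion.** The point holds for the De Novo HCC endpoint. Followed as written, the SAP censors as HCC-free a participant whose death record names HCC but whose liver disease assessment page does not, and this can only lower the primary HCC estimate. It does not hold as a general claim that decompensation events are lost.

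The actual size cannot be derived from the documents. It depends on how many participants died before their next visit with newly diagnosed HCC, and on whether sites completed the page from records. Under the assumptions above, the loss would be at most about 4% to 20% of HCC events for death hazards of 0.2 to 1.0 per year, or 8.8% recorded as 8.4% to 7.1% at 2% per year. The change is worth making because it concerns a primary endpoint, the error has a known direction, and the data needed are largely collected already.

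**What to change.** 1. Add to SAP 6.1.3.2.1 that HCC given in the cause-of-death record counts as De Novo HCC when no HCC preceded registry start, dated at diagnosis if known and otherwise at death. Alternatively, present this as a sensitivity analysis beside the planned estimate.
2. Report the number of deaths with no liver disease assessment covering the final interval, so that a reader can judge how large the gap could be.
3. Where feasible, state that the existing page is completed from available records when a participant dies, covering the time from the last visit to death.

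The first two items need no visit or procedure. The immediate cause of death is already collected where available and reviewed by Clinical Research. SAP 1 provides for changes after SAP finalization to be documented in the CSR. The third item costs one existing eCRF page per death and, at this stage, probably retrospective retrieval of records, some of which will not be obtainable.

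The downside is small. Only the immediate cause is described as collected, so a participant with HCC whose death is recorded under another terminal event would still be missed, and some HCC events would be dated at death, later than their diagnosis.

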### 6.3.6. Endoscopy

An endoscopy will be performed to evaluate for varices at Day 1 (+/- 6 months) and within 6 months prior to Week 240. There is no need to repeat if subject has available endoscopy results performed within 6 months prior to Day 1 or Week 240 as part of standard of care. The results of the endoscopy will be recorded into the clinical database.

### 6.3.7. Transient Elastography

A transient elastography will be performed to assess the liver at Day 1 (+ 4 weeks) and every 48 weeks (+/- 4 weeks) through Week 240 at sites with a Fibroscan®. The results of the scan will be recorded into the clinical database.

### 6.3.8. CCI

CCI

### 6.3.9. MELD Score and Child-Turcotte-Pugh Score

Model for End-Stage Liver Disease (MELD) Score and Child-Turcotte-Pugh (CTP) data will be calculated at each visit.

For the components of the MELD score and the components of the CTP score which are based on laboratory values, the data will be obtained from the central laboratory, and the scores will be calculated within the clinical database.

### 6.3.10. CCI

CCI

## 7. ADVERSE EVENTS MANAGEMENT

### 7.1. Adverse Events

This study is a long-term observational Registry in which no study medication will be administered. Adverse events related to the Gilead-sponsored treatment protocol will be followed in accordance with that protocol. Adverse events related to an all-oral SOF-based regimen used outside a clinical study should be reported as described in the locally approved product information utilizing the usual means for spontaneous reporting.

As a consequence, adverse event reporting in this Registry will be restricted to the following:

- Any adverse event occurring as a consequence of procedures required by this Registry protocol will be followed and documented in accordance with provisions outlined below.

For purposes of this Registry, an **adverse event** (AE) is any untoward medical occurrence in a clinical study subject associated with procedures required by this Registry protocol. An AE can therefore be any unfavorable and/or unintended sign, symptom, or disease temporally associated with procedures required by this Registry (e.g., hematoma following venipuncture).

An AE does not include the following for this Registry:

- Any medical condition or clinically significant laboratory abnormality with an onset date before the consent form is signed and before Day 1 visit is not an AE.
- Any medical condition or clinically significant laboratory abnormality with an onset date after the consent form is signed that is related to the Gilead-sponsored treatment protocol or to an all-oral SOF-based regimen used outside a clinical study.

### 7.2. Serious Adverse Events

Any **serious adverse event** (SAE) occurring during the Gilead-sponsored treatment protocol will be followed, documented and reported under that treatment protocol. Similarly, any new SAEs occurring while the subject is participating in the Registry that are considered to be related to the study drugs administered or procedures in the treatment protocol will be followed, documented and reported under the Gilead-sponsored treatment protocol or as per locally approved product information. Any serious adverse event related to an all-oral SOF-based regimen used outside a clinical study should be reported as described in the locally approved product information utilizing the usual means for spontaneous reporting.

The only SAEs that will be reported under this Registry are events considered to be related to procedures required by the Registry protocol. A **serious adverse event** is defined as follows:

Any adverse event that results in any of the following outcomes:

- Death
- Life-threatening (the subject was at **immediate** risk of death at the time of the event; it does not refer to an event that hypothetically might have caused death if it were more severe)

- In-patient hospitalization or prolongation of existing hospitalization (excluding, for example, those for study therapy or placement of an indwelling catheter, unless associated with other SAEs)
- Persistent or significant disability/incapacity
- Congenital anomaly/birth defect in the offspring of a subject who received investigational medicinal product. All pregnancy events will be followed to resolution/outcome in the Gilead-sponsored treatment protocol
- Other: medically significant events that may not be immediately life-threatening or result in death or hospitalization, but based upon appropriate medical and scientific judgment, may jeopardize the subject or may require medical or surgical intervention to prevent one of the outcomes listed above

### **Clarification of Serious Adverse Events**

- Death is an outcome of an AE, and not an adverse event in itself.
- “Life-threatening” means that the subject was at immediate risk of death from the event as it occurred. This does not include an event that might have led to death if it had occurred with greater severity.
- “In-patient hospitalization” means the subject has been formally admitted to a hospital for medical reasons, for any length of time. This may or may not be overnight. It does not include presentation and care within an emergency department.

The relationship to study procedures (e.g., invasive procedures such as venipuncture) should be assessed using the following considerations:

- **No:** Evidence exists that the AE has an etiology other than the study procedure.
- **Yes:** The AE occurred as a result of protocol required procedures such as venipuncture.

## **7.3. Serious Adverse Event Reporting Requirements**

### **7.3.1. All Serious Adverse Events**

Gilead Sciences is required to expedite to worldwide regulatory authorities reports of SAEs, Serious Adverse Drug Reactions (SADRs) or Suspected Unexpected Serious Adverse Reactions (SUSARs) in line with relevant legislation, including the applicable US FDA Code of Federal Regulation, the European Commission Clinical Trials Directive (2001/20/EC); therefore, Gilead Sciences (or the CRO on the behalf of Gilead Sciences) must be notified immediately regarding the occurrence of any SAE or SADR that occurs after the subject consents to participate in the Registry, including SAEs/SADRs resulting from protocol-required procedures as defined in relevant legislation including 2001/20/EC, performed from Day 1 onwards. The procedure for reporting SAEs is as follows:

- All AEs and SAEs will be recorded in the electronic case report form (eCRF) database within the timelines outlined in the eCRF completion guideline.

